6.5 Overdose

An overdose is defined as the accidental or intentional administration of any dose of a product that is considered both excessive and medically important. All occurrences of overdose must be reported as an SAE (see Section 6.1.1 for reporting details.).

6.6 Potential Drug Induced Liver Injury (DILI)

Wherever possible, timely confirmation of initial liver-related laboratory abnormalities should occur prior to the reporting of a potential DILI event. All occurrences of potential DILIs, meeting the defined criteria, must be reported as SAEs (see Section 6.1.1. for reporting details).

Revised Protocol No.: 01

Potential drug induced liver injury is defined as:

• AT (ALT or AST) elevation > 3 times upper limit of normal (ULN)

AND

• Total bilirubin > 2 times ULN, without initial findings of cholestasis (elevated serum alkaline phosphatase)

AND

• No other immediately apparent possible causes of AT elevation and hyperbilirubinemia, including, but not limited to, viral hepatitis, pre-existing chronic or acute liver disease, or the administration of other drug(s) known to be hepatotoxic.

6.7 Other Safety Considerations

Any significant worsening noted during interim or final physical examinations, electrocardiogram, x-ray filming, any other potential safety assessment required or not required by protocol should also be recorded as a nonserious or serious AE, as appropriate, and reported accordingly.

7 DATA MONITORING COMMITTEE AND OTHER EXTERNAL COMMITTEES

Not applicable.

8 STATISTICAL CONSIDERATIONS

8.1 Sample Size Determination

This trial is an estimation trial. Sample size in this study will be approximately 40 subjects per cohort and is not based on power considerations. Tables below provide the 95% confidence intervals computed from different observed rates. Those tables indicate what would be the reliability of the AE rate estimates for N=40 (Table 8.1-1) and N=35 (see Table 8.1-2) treated subjects. A threshold of 45% will be applied to the upper limit of the confidence interval as an informal guideline for high toxicity

Thirty-five subjects per cohort will be the minimum number of subjects receiving treatment in Induction Period 2. For that purpose, randomization will stay open until at least 40 subjects in each cohort have been treated with at least one dose of study treatment in Induction Period 1 and 35 subjects in each cohort have received at least one dose of study treatment in Induction Period 2. Assuming a drop-out rate during induction period 1 would be at most 12.5%, at least 35 subjects would be treated in induction period 2 if 40 subjects are to be randomized per cohort.

Table 8.1-1: Exact 95% CI width and upper bound for AE rates up to 40% when observed in 40 subjects

Nb Subj with Rel Gr3-5 A	Rate of Rel Gr3-5 AE	Exact 95% CI width	Upper limit Exact 95%CI
4	10%	21%	23.7%
8	20%	27%	35.6%
10	25%	29%	41.2%
11	27.5%	29%	43.9%
12	30%	30%	46.5%
13	32.5%	31%	49.1%
14	35%	31%	51.7%
16	40%	32%	57%

Table 8.1-2: Exact 95% CI width and upper bound for AE rates up to 40% when observed in 35 subjects.

Nb Subj with Rel Gr3-5 AE	Rate of Rel Gr3-5 AE	Exact 95% CI Width	Upper Limit Exact 95%CI
4	11.4%	23.5%	26.7%
7	20%	28.5%	36.9%
9	25.7%	30.8%	43.3%
10	28.6%	31.7%	46.3%
11	31.4%	32.4%	49.3%
14	40%	34%	57.9%

8.2 Populations for Analyses

All Enrolled Subjects: All subjects who signed an informed consent form and were registered into the IVRS.

All Randomized Subjects: All subjects who were randomized to any cohort in the study.

All Treated Subjects: All subjects who received at least one dose of study medication.

8.3 Endpoints

8.3.1 Primary Endpoint

The primary endpoint of the study is the rate of treatment-related Grade 3-5 AEs during the Induction Period (Periods 1 and 2) in subjects receiving sequential induction treatment with either nivolumab followed by ipilimumab or ipilimumab followed by nivolumab.

The treatment-related Grade 3 - 5 AEs rate is defined as number of subjects who experienced at least 1 treatment related Grade3 - 5 adverse event (per NCI CTCAE v 4.0 criteria, any PT terms) with an onset date after or on first day of the Induction Period and not later than discontinuation date from the Induction Period, divided by number of treated subjects. AEs with an onset date after start of subsequent anti-cancer therapy, or start date of Continuation Period treatment will not be included.

- For subjects who discontinue Induction Period early and enter the Follow-Up Period, AEs that occur in Follow-Up, including those before Week 25, will not be included in the primary endpoint.
- For subjects who discontinue treatment before the end of Induction Period 1 or 2 but who are eligible to enter the next study period, AEs that occur before end of Induction Period 2 will be included in the primary endpoint, even if they occur after dosing ends while they are waiting to enter the next study period.

Primary and secondary endpoint analysis will be performed when at least 40 subjects per cohort have completed/discontinued Induction Period 1 and at least 35 subjects per cohort have completed/discontinued Induction Period 2 and all treated subjects with an objective response at Week 25 have been followed through study Week 33 in order to confirm disease response.

8.3.2 Secondary Endpoints

Secondary endpoints will be analyzed at the time of the primary endpoint analysis. Duration of response from Week 25 will be re-assessed at time of the OS update analysis.

8.3.2.1 Response Rate at Week 25

Response rate at Week 25 is defined as the number of subjects who have a complete response (CR) or partial response (PR) at Week 25, with confirmation at scheduled scan at Week 33, divided by the total number of randomized subjects. Note that the results of the tumor assessment at Week 13 will not be considered in the assessment of response rate at Week 25. This means, for example, that subjects with progressive disease at Week 13 are not precluded from having an assessment of CR or PR at Week 25 for this endpoint if the scan at Week 25 demonstrates such a response.

Duration of response (DOR) from Week 25 will also be assessed for subjects with confirmed response at Week 25 (see definition above). DOR is defined as the time between the Week 25 assessment date and the date of objectively documented disease progression (taking as reference

the smallest sum of diameters of target lesions beginning at Week 25) or death, whichever occurs first.

8.3.2.2 Progression Rates at Weeks 13 and 25

Progression rate at a specific timepoint is defined as the number of subjects who have Progressive Disease (PD) per RECIST 1.1 at that specific timepoint divided by the total number of randomized subjects.

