The treatment-related Grade 3 - 5 AEs rate is defined as number of subjects who experienced at least 1 treatment related Grade3 - 5 adverse event (per NCI CTCAE v 4.0 criteria, any PT terms) with an onset date after or on first day of the induction period and not later than discontinuation date from the Induction Period, divided by number of treated subjects. AEs with an onset date after start of subsequent anti-cancer therapy, or start date of Continuation Period treatment will not be included. For subjects who discontinue Induction Period early and enter the Follow-Up Period, AEs that occur in Follow-Up, including those before Week 25, will not be included in the primary endpoint. For subjects who discontinue treatment before the end of Induction Period 1 or 2 but who are eligible to enter the next study period, AEs that occur before end of Induction Period 2 will be included in the primary endpoint, even if they occur after dosing ends while they are waiting to enter the next study period.

The secondary endpoints are Response Rate at Week 25 and Progression Rates at Weeks 13 and 25. Subjects will be assessed for response via tumor assessments (CT or MRI) prior to dosing at Weeks 13, 25, 33, 41, 49 (+/- 1 weeks) and then every 12 weeks. Response rate at Week 25 is defined as the number of subjects who have a complete response (CR) or partial response (PR) at Week 25 (regardless of the tumor assessment at Week 13), with confirmation at scheduled scan at Week 33, divided by the total number of randomized subjects. Progression rates at Weeks 13 and 25 are defined as the number of subjects who have Progressive Disease (PD) per RECIST 1.1 at the specific timepoint (Week 13 or Week 25) divided by the total number of randomized subjects.

Statistical Considerations:

Sample Size: This trial is an estimation trial. Sample size in this study will be approximately 40 subjects per cohort and is not based on power considerations. Tables below provide the 95% confidence intervals computed from different observed rates. Those tables indicate what would be the reliability of the AE rate estimates for N=40 (Table 8.1-1) and N=35 (Table 8.1-2) treated subjects. A threshold of 45% will be applied to the upper limit of the confidence interval as an informal guideline for high toxicity

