3.1.3 Follow-Up Period

- Begins when the decision is made to discontinue a subject from study treatment or the subject has completed 2 years of study therapy from the first study treatment in Induction Period 1 (no further treatment with either nivolumab or ipilimumab)
- For subjects who have NOT progressed, tumor assessments will continue as scheduled at Weeks 13, 25, 33, 41 and then starting at Week 49 every 12 weeks until documented progression.
- Subjects will be followed for all toxicities until these toxicities resolve, return to baseline or are deemed irreversible. All AEs will be documented for a minimum of 100 days after last dose of study treatment.

After completion of the two "X" follow-up visits (Table 5.1-5) subjects will be followed every 3 months (by clinic visit or telephone contact) for survival and report of any subsequent anti-cancer treatments for up to 5 years from the first dose of study treatment in Induction Period 1 until death, loss to follow-up, or withdrawal of consent.

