4.3.6 Nivolumab and/or Ipilimumab Treatment Discontinuation Criteria

4.3.6.1 Permanent Discontinuation Criteria for Both Nivolumab and Ipilimumab

All further study treatment (both nivolumab and ipilimumab) must be permanently discontinued if any of the following occurs during treatment with either nivolumab or ipilimumab:

Any Grade 4 drug-related adverse event or laboratory abnormality, except for the following events which do not require discontinuation

- Grade 4 neutropenia \leq 7 days
- Grade 4 lymphopenia or leukopenia
- Isolated Grade 4 electrolyte imbalances/abnormalities that are not associated with clinical sequelae and are corrected with supplementation/appropriate management within 72 hours of their onset
- Any drug-related adverse event which requires treatment with any immunosuppressive therapy other than corticosteroids (eg, infliximab, mycophenylate)
- Any adverse event, laboratory abnormality, or intercurrent illness which, in the judgment of the Investigator, presents a substantial clinical risk to the subject with continued dosing of nivolumab or ipilimumab
- Clinical or radiographic progression associated with rapid clinical deterioration which, in the judgment of the Investigator, is unlikely to benefit from further study treatment (nivolumab or ipilimumab).

4.3.6.2 Permanent Discontinuation Criteria for One Study Treatment (Discontinuation of Nivolumab Only or Discontinuation of Ipilimumab Only)

If any of the following occurs during treatment with either nivolumab or ipilimumab, treatment with **that particular drug** must be permanently discontinued:

- Any Grade 2 drug-related uveitis or eye pain or blurred vision that does not respond to topical therapy and does not improve to Grade 1 severity within the re-treatment period OR requires systemic treatment
- Any Grade 3 non-skin, drug-related adverse event lasting > 7 days, with the following exceptions for laboratory abnormalities, drug-related uveitis, pneumonitis, bronchospasm, colitis, diarrhea, hypersensitivity reactions, and infusion reactions:
- Grade 3 drug-related uveitis, pneumonitis, bronchospasm, diarrhea, colitis, hypersensitivity reaction, or infusion reaction of any duration requires discontinuation
- Grade 3 drug-related laboratory abnormalities do not require treatment discontinuation except:
- Grade 3 drug-related thrombocytopenia > 7 days or associated with bleeding requires discontinuation

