5.4.6.1 Missing Assessments and Not Evaluable Designation

When no imaging/measurement is done at all at a particular time point, the subject is not evaluable (NE) at that time point. If only a subset of lesion measurements are made at an assessment, the case is also considered NE at that time point, unless a convincing argument can be made that the contribution of the individual missing lesion(s) would not have changed the assigned time-point response.

[figure not shown]

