8.4.3 Efficacy Analyses

8.4.3.1 Response Rate at Week 25

Response rate at Week 25 will be computed by cohort using all randomized subjects. Response rate estimates and corresponding 95% CIs will be calculated using the Clopper-Pearson method.

As sensitivity analysis, response rates including only those subjects who were response evaluable at Week 25 (ie, those subjects with a tumor assessment at Week 25) will also be calculated.

8.4.3.2 DOR from Week 25

Duration of response from Week 25 will be assessed for subjects with confirmed response at Week 25. Median DOR estimate and corresponding 95% CIs will be provided for cohort using the Kaplan-Meier methodology

8.4.3.3 Progression Rates at Weeks 13 and 25

Progression rates at Week 13 and at Week 25 will be computed by cohort using all randomized subjects. Progression rate estimates and corresponding 95% CIs will be calculated using the Clopper-Pearson method.

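### The Week 13 and Week 25 progression rates score a subject who died before the scan, or progressed earlier and was not scanned, the same as a subject who has not progressed

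*Protocol*

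**What the plan says.** Section 8.3.2.2 defines the progression rate at a timepoint as the number of "subjects who have Progressive Disease (PD) per RECIST 1.1 at that specific timepoint divided by the total number of randomized subjects". The synopsis gives the same definition: "Progression rates at Weeks 13 and 25 are defined as the number of subjects who have Progressive Disease (PD) per RECIST 1.1", at Week 13 or Week 25, over all randomized subjects. Section 8.4.3.3 fixes the analysis set: "Progression rates at Week 13 and at Week 25 will be computed by cohort using all randomized subjects", with Clopper-Pearson intervals.

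None of these places adds death, or PD documented before the visit, to the numerator. On missing scans, Section 5.4.6.1 says: "When no imaging/measurement is done at all at a particular time point, the subject is not evaluable (NE) at that time point".

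Two neighbouring provisions differ. DOR in Section 8.3.2.1 ends at progression measured from "the smallest sum of diameters of target lesions beginning at Week 25) or death, whichever occurs first", so death is an event there. Section 8.4.3.1 gives the response rate a sensitivity analysis in subjects with a Week 25 scan. The progression rate has neither provision.

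**The concern.** Dividing by all randomized subjects is conservative for a response rate, because the dead and the unscanned count as failures. For a progression rate the same convention works the other way: the dead and the unscanned count as if they had not progressed. These two rates are the only secondary measure of progression in each cohort, and readers will set them side by side to judge which sequence controls disease better early on. A cohort that loses more subjects to early death is rewarded with a lower rate.

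The subjects most exposed are those taken off both drugs under Section 4.3.6.1 for "Clinical or radiographic progression associated with rapid clinical deterioration". They enter Follow-Up, where the protocol does not agree with itself on whether they are scanned at Weeks 13 and 25.

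**Working it through.** **Scoring under the stated rule**

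| Subject's course | In numerator? | In denominator? |
|---|---|---|
| PD on the scan at the visit | Yes | Yes |
| Scanned at the visit, no PD | No | Yes |
| Died before the visit | No | Yes |
| PD documented earlier, no scan at the visit (NE) | No | Yes |

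The last three rows have the same effect on the rate.

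**Who is scanned at Weeks 13 and 25**

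- Sections 3.1.2.1 and 3.1.2.2 require the Week 13 and Week 25 scans of all subjects, including those who stopped treatment early.
- Table 5.1-5 lists Week 25 in Follow-Up. The row itself carries no restriction by progression status, but it refers to Section 5.4.
- Section 3.1.3 covers only Follow-Up subjects still free of progression. Its rule for that group reads: "tumor assessments will continue as scheduled at Weeks 13, 25, 33, 41 and then starting at Week 49 every 12 weeks until documented progression".
- Section 5.4 limits Follow-Up scans to subjects who stopped for reasons other than PD. The visits it then lists start at Week 33, and its Induction paragraph has no such limit, so it does not itself cancel the Week 13 and 25 scans.

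A subject who stopped early for progression therefore comes under conflicting instructions. No scan rule helps for a subject who has died.

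**Inputs:** about 40 subjects per cohort and at most 12.5% drop-out in Induction Period 1 (Section 8.1); median OS 20 months in both cohorts (Section 3.1.4).

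**Checks against the plan's own figures**

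- Clopper-Pearson upper limit for 12/40: 46.5%, as in Table 8.1-1.
- 40 × (1 − 0.125) = 35, as in Section 8.1.
- Exponential OS with hazard λ = ln 2 / 20 per month, uniform accrual over 12 months and 24 months of further follow-up: deaths = 1 − (e^(−24λ) − e^(−36λ)) / (12λ) = 64.4%, against approximately 65% in Section 3.1.4.

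**Size per subject:** 1/40 = 2.5 points.

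**Week 13, from the drop-out assumption:** 12.5% × 40 = 5 subjects. If everyone dead or gone without a Week 13 scan is among those 5, the shortfall is between 0 and 5 × 2.5 = 12.5 points, and smaller to the extent that drop-outs had not progressed. The protocol gives no comparable figure for Week 25.

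**Deaths before the visit, assuming a constant hazard:** P = 1 − e^(−λt), with t = 2.76 months (12 weeks) and 5.52 months (24 weeks).

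| Hazard | Dead by Week 13 | Dead by Week 25 |
|---|---|---|
| Full (median 20 months) | 9.1% (3.6 of 40) | 17.4% (7.0 of 40) |
| Half | 4.7% (1.9 of 40) | 9.1% (3.6 of 40) |
| Quarter | 2.4% (0.9 of 40) | 4.7% (1.9 of 40) |

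Even at a quarter of the hazard, the chance of at least one death by Week 25 in a cohort of 40 is 1 − (1 − 0.0467)^40 = 85%.

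**Illustration with assumed counts.** Both cohorts have 20 of 40 subjects progressed or dead at Week 25. One has 3 deaths among the 20, the other 7.

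| Rate at Week 25 (95% CI) | 3 deaths | 7 deaths | Gap |
|---|---|---|---|
| Current rule | 17/40 = 42.5% (27.0–59.1) | 13/40 = 32.5% (18.6–49.1) | 10.0 points |
| Evaluable only | 17/37 = 45.9% (29.5–63.1) | 13/33 = 39.4% (22.9–57.9) | 6.6 points |
| Progression or death | 20/40 = 50% (33.8–66.2) | 20/40 = 50% (33.8–66.2) | 0 |

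The current rule favours the cohort with more deaths. Restricting to evaluable subjects narrows the gap without closing it, because it also leaves the deaths out.

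**The case against.** The definition is explicit and repeated consistently, and a radiographic rate at a fixed visit is a legitimate quantity. Supplementary analyses and NE tables are commonly left to a SAP, which is not at hand. DOR is a time-to-event measure in responders, so its treatment of death is no formal contradiction. Deaths appear elsewhere: OS is an exploratory endpoint with a planned update, and treatment-related Grade 5 events are in the primary endpoint. Few subjects should progress early and go unscanned, because progressors stay on treatment through each Induction Period unless they deteriorate rapidly. The size rests on assumptions: the 12.5% concerns subjects not reaching Induction Period 2 treatment rather than missing scans, the 3-versus-7 split is chosen, and the intervals overlap widely.

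Most of this limits the size and leaves the direction intact. The 12.5% anchor is not a strict bound, the group that progressed early and was not scanned is probably small, and the effect of Section 5.4 on the scan schedule can be argued. But a SAP cannot count deaths in this rate without changing the endpoint the protocol defines, and reporting OS separately does not change how the rate is scored. The exploratory-endpoint text is not shown, so a progression-or-death measure may exist there; that would not change this endpoint either.

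**Conclusion.** The concern holds. As defined, the Week 13 and Week 25 progression rates are biased downward as measures of treatment failure, by 2.5 points for each subject at 40 per cohort who died before the visit or progressed earlier and was not scanned. That direction follows from the text alone.

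The total is uncertain. The drop-out assumption suggests 0 to 12.5 points at Week 13. The constant-hazard assumption suggests about 2 to 9 points at Week 13 and 5 to 17 at Week 25 from deaths, over a quarter to the full hazard. These are illustrations and not bounds, and a lower early hazard would reduce them further.

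Only descriptive secondary estimates and their intervals are affected. The primary endpoint and its informal 45% guideline are not. This should be fixed, but it does not threaten the trial's main result.

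**What to change.** In the synopsis and Sections 8.3.2.2 and 8.4.3.3:

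1. Keep the current rate, but label it as PD on the scan at the visit.
2. Report beside it a progression-or-death rate at Week 13 and at Week 25. The numerator is subjects with PD on the scan at that visit, plus subjects who died before it, plus subjects with earlier documented PD and no scan at that visit. The denominator is all randomized subjects.
3. State that a subject scanned at the visit takes the status of that scan. A Week 13 progressor who responds at Week 25 is then not a Week 25 progressor, in keeping with Section 8.3.2.1.
4. Show deaths and other NE subjects per cohort. Subjects with clinical progression only, and those withdrawn or lost without documented PD, stay outside the composite numerator, so this count is where they become visible.
5. An evaluable-only rate parallel to Section 8.4.3.1 may be added, but not in place of the composite.

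Separately, reconcile Section 3.1.3 with Sections 3.1.2.1 and 3.1.2.2 and Table 5.1-5 on who is scanned at Weeks 13 and 25, and align the Follow-Up paragraph of Section 5.4 with the result.

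The cost is wording plus one table; death and PD dates are already collected. The downside is that the composite counts deaths from any cause, including treatment-related Grade 5 events already in the primary endpoint, and the rates will look less favourable.

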8.4 Analyses

8.4.1 Demographics and Baseline Characteristics

Demographics and baseline laboratory results will be summarized by cohort as randomized using descriptive statistics for all randomized subjects.

8.4.2 Primary Endpoint Analysis

Rate of treatment-related Grade 3-5 AEs during the induction period will be computed by treatment cohort using all treated subjects. Corresponding 95% CIs will be calculated using the Clopper-Pearson method.

As sensitivity analysis, rates and 95% CI will be also computed using the subset of subjects who received at least one dose of study treatment in Induction Period 2.

8.4.3 Efficacy Analyses

8.4.3.1 Response Rate at Week 25

Response rate at Week 25 will be computed by cohort using all randomized subjects. Response rate estimates and corresponding 95% CIs will be calculated using the Clopper-Pearson method.

As sensitivity analysis, response rates including only those subjects who were response evaluable at Week 25 (ie, those subjects with a tumor assessment at Week 25) will also be calculated.

8.4.3.2 DOR from Week 25

Duration of response from Week 25 will be assessed for subjects with confirmed response at Week 25. Median DOR estimate and corresponding 95% CIs will be provided for cohort using the Kaplan-Meier methodology

8.4.3.3 Progression Rates at Weeks 13 and 25

Progression rates at Week 13 and at Week 25 will be computed by cohort using all randomized subjects. Progression rate estimates and corresponding 95% CIs will be calculated using the Clopper-Pearson method.

